4.13.4. Vital Signs

The actual value and change from Baseline will be summarized for vital signs (temperature, heart rate, respiratory rate, and systolic and diastolic blood pressure) descriptively at Baseline and other study time points.

By-patient listings of vital sign measurements will also be provided.

4.13.5. Electrocardiogram

ECG results will be summarized descriptively, including the number and percent of patients with normal, abnormal, and clinically significant abnormal results at Baseline and each study time point.

In addition, an ANCOVA model including CFB in various ECG parameters at Week 52 (i.e., corrected QT [Bazett and Fridericia], RR interval, PR interval, QRS duration, Heart Rate) as the dependent variable, treatment as a fixed effect, and baseline ECG parameter value, will be used to assess the treatment difference in the ECG parameters at Week 52.

Treatment group differences in heart rate will be compared via an MMRM ANCOVA model with treatment, baseline heart rate, visit, visit×treatment (interaction term), and baseline heart

rate×treatment (interaction term) as fixed effects and patient as a random effect. In this model, visit is a categorical variable, treatment is a dichotomous variable, and baseline heart rate is a continuous variable. This analysis will be performed on the Safety Population.

This repeated-measures analysis will be based on the restricted maximum likelihood method assuming an unstructured covariance structure to model the within-patient errors. A Kenward-Roger approximation will be used for the denominator degrees of freedom. If there is a convergence problem due to the unstructured covariance matrix, a compound symmetry covariance structure will be used to model the within-patient variance; if the compound symmetric covariance structure fails to converge, a variance components approach will be applied.

All ECG data for each patient will be provided in data listings.

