#### **6.7. Cardiac Monitoring**

Patients with DMD are known to have resting tachycardia even in the age range in this clinical study ([Thomas, 2012](#)). Additionally, decreases in heart rate variability have been observed ([Thomas, 2015](#)). Since decreases in heart rate to age-normative values were observed in a previous clinical study (CAT-1004-201), measures of heart rate and variability will be collected for approximately 48 hours via a wearable cardiac monitoring device if approved for use in the participating country. In addition, the results from the patient's last cardiac assessment should be documented as part of

medical history. Prospective cardiac assessments performed should also be documented as part of ongoing procedures.

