4.2.4. Adjustments for Covariates

Statistical models will adjust for the stratification variables as covariates.

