4.10.1. Primary Efficacy Analysis

The primary efficacy endpoint is the CFB in the NSAA Total Score at Week 52. NSAA Total Scores and the CFB values will be summarized by treatment group and time point using descriptive statistics.

If a patient initiates corticosteroid therapy or discontinues study treatment, all observations from that patient after these events will be censored from the primary efficacy analyses.

The primary efficacy endpoint analysis will be an MMRM ANCOVA. The MMRM model will include:

- CFB in the NSAA Total Score as the dependent variable
- Variables in the Model

Visit (a categorical variable)	
Treatment (edasalonexent or placebo)	Treatment \times Visit
Region (North America vs. Europe/Asia/Australia)	Region \times Visit
Baseline age (as a continuous variable),	Baseline Age \times Visit
Baseline time to stand from supine (as a continuous variable)	Baseline time to Stand \times Visit
Baseline NSAA score (as a continuous variable)	Baseline NSAA score \times Visit

- Patient as a random effect.

The primary efficacy analysis will test the difference between the edasalonexent versus placebo at Week 52 using this MMRM model.

Sample SAS code for the primary efficacy analysis is provided in [APPENDIX 1: Sample MMRM Code](#).

Descriptive summary statistics including number of patients, mean, standard error, least-square means (LS means), LS means differences, along with the p-values and corresponding 95% CIs

will be provided. Specifically, the primary efficacy endpoint hypothesis test of no treatment difference between edasalonexent and placebo is based on the least-squares means (LS-means) difference and corresponding p-value from the Week 52 visit. The results for the treatment difference for the other visits will also be provided to assess the consistency of treatment effect over different visits.

The repeated-measures analysis will be based on the restricted maximum likelihood method assuming an unstructured covariance structure to model the within-patient errors. A Kenward-Roger approximation will be used for the denominator degrees of freedom. If there is a convergence problem due to the unstructured covariance matrix, a compound symmetry covariance structure will be used to model the within-patient variance; if the compound symmetric covariance structure fails to converge, a variance components approach will be applied.

The primary efficacy endpoint analysis is an observed case analysis, with no imputation of missing data.

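### SAP 4.13.5 leaves the heart-rate MMRM contrast undefined, with an uncentred baseline×treatment term in place of baseline×visit, and both ECG models omit the strata that SAP 4.2.4 calls for

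*SAP*

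**What the plan says.** SAP 4.13.5 describes two inferential ECG analyses.

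- **Heart-rate MMRM.** The model lists arm, visit, their interaction and the baseline value as effects, and its last term crosses the baseline with arm: "rate×treatment (interaction term) as fixed effects and patient as a random effect". On scale, the section adds: "In this model, visit is a categorical variable, treatment is a dichotomous variable, and baseline heart rate is a continuous variable". No centring is mentioned, and no baseline×visit term is listed. The estimation details (REML, unstructured covariance, Kenward-Roger, fallback structures) match those of SAP 4.10.1. The sentence in 4.10.1 that ties the test to the LS-means difference at Week 52 has no counterpart here.
- **Week 52 ANCOVA.** It covers QTc, RR, PR, QRS and heart rate, with "treatment as a fixed effect, and baseline ECG parameter value, will be used to assess the treatment difference in the ECG parameters at Week 52". No other covariate is listed.

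SAP 4.2.4 gives a general rule with no restriction to efficacy: "Statistical models will adjust for the stratification variables as covariates". The strata in SAP 2.2 are age, time to stand, eteplirsen treatment and region.

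SAP 4.13 makes safety comparisons qualitative apart from named exceptions, of which these are two. Protocol 6.7 gives the background for heart rate: "Since decreases in heart rate to age-normative values were observed in a previous clinical study".

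**The concern.** Once a continuous baseline is crossed with treatment, there is no longer one treatment effect; there is one for each baseline value. Unless the plan fixes that value, the treatment main effect refers to a baseline of zero, which no child can have. The section names neither the contrast nor the visit, so two competent programmers could report very different p-values from the same model.

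Heart-rate lowering is a known signal for this drug, and heart rate is one of the few safety variables given a formal comparison. Week 52 heart rate is also tested twice, by the ANCOVA and by the MMRM, with neither named as the main analysis.

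The covariate lists conflict with SAP 4.2.4. SAP Section 6 mentions no exception.

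**Working it through.** The plan gives no figure for the ECG models, so there is none to reproduce.

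**1. What the treatment term estimates.** In the model as written, the arm difference at visit v and baseline x is

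D_v(x) = τ + θ_v + γx,

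where τ is treatment, θ_v is visit×treatment and γ is baseline×treatment. The treatment coefficient and its Type 3 test set x = 0. An LS-means difference at default settings sets x to the mean baseline.

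**2. Loss of precision at x = 0.** The variance of D(x) is approximately proportional to 1 + ((x − mean)/SD)². The ratio of the SE at 0 to the SE at the mean is therefore √(1 + (mean/SD)²). The documents give no baseline heart-rate mean or SD, so both are assumed:

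| Mean (beats/min) | SD 8 | SD 10 | SD 12 | SD 15 |
|---|---|---|---|---|
| 90 | 11.29 | 9.06 | 7.57 | 6.08 |
| 100 | 12.54 | 10.05 | 8.39 | 6.74 |
| 110 | 13.79 | 11.05 | 9.22 | 7.40 |

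**3. Simulation check.** Numbers: 126 × 0.8 = 100.8 at 2:1, rounded to 67 and 34. Assumed: baseline mean 100, SD 12; baseline slope −0.5; two post-baseline visits with one record each, residual SD 10, correlation 0.6; true effect −5 beats/min; no interaction. There were 2,000 runs, analysed by generalised least squares with known covariance and critical value 1.96.

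| Test | SE | Rejection |
|---|---|---|
| As written, Type 3 treatment (x = 0) | 16.4 | 0.065 |
| As written, Week 52 LS-means at mean baseline | 2.12 | 0.689 |
| Baseline×visit instead, Type 3 treatment | 1.89 | 0.767 |
| Baseline×visit instead, Week 52 LS-means | 2.12 | 0.685 |

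By hand, the visit-averaged variance is (100 + 100 + 2×60)/4 = 80, so the SE at the mean is √(80 × (1/67 + 1/34)) = 1.88. Times 8.39 this is 15.8, close to the simulated 16.4. With no true effect, all four tests reject about 4.5% of the time, so the issue is power and meaning rather than false positives.

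**4. The sign can change.** If children with higher baselines fall more, say γ = −0.2 per beat, the effect at 0 is −5 + (−0.2)(0 − 100) = +15, against −5 at the mean. The simulation gave +15.2 and −5.0.

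**5. Effect of leaving out baseline×visit.** With baseline slopes of −0.3 and −0.6 at the two visits and complete data, the Week 52 LS-means difference was −4.99 with either interaction. No bias appeared. Incomplete data were not examined.

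**6. Covariates side by side.**

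| Model | Age | Time to stand | Region | Baseline crossed with |
|---|---|---|---|---|
| Primary MMRM (4.10.1), reused in 4.10.2 and for strength and PUL in 4.10.3 | yes | yes | yes | visit |
| PODCI and rank-sum ANCOVAs (4.10.3) | yes | yes | yes | not applicable |
| Heart-rate MMRM (4.13.5) | no | no | no | treatment |
| ECG ANCOVAs (4.13.5) | no | no | no | not applicable |

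Eteplirsen appears in none of them. The efficacy models have a reason: SAP 3.1 removes those patients from the FAP. The Safety Population, used for the ECG analyses, keeps them.

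**The case against.** The strongest reply is that the section never says the test is the treatment coefficient. It says arms are compared through a model containing visit×treatment, for which by-visit contrasts are the natural output. The only MMRM contrast the SAP defines, in 4.10.1, is an LS-means difference. This largely stands.

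A reader might infer that the planned heart-rate test is a test at 0 beats/min and so almost powerless; with 84 and 42 patients, the simulated rejection rates are 0.054 at zero and 0.838 for the visit-averaged contrast with baseline×visit. The documents do not support that inference. They leave the contrast open, the rates rest on assumed inputs, and under the LS-means reading the choice of interaction makes almost no difference.

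Other points also carry weight:

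- The baseline×treatment term may be deliberate, since Protocol 6.7 reports a fall towards normal values in children with resting tachycardia. A slip for baseline×visit is plausible but unproven.
- The Week 52 ANCOVA has no interaction, so it already gives a sound comparison. Running it beside an MMRM is not an error; SAP 4.10.4 does this for the primary endpoint, though there it is labelled a sensitivity analysis.
- SAP 4.2.4 may have been meant for efficacy models only. Its wording does not say so.
- The sample code in SAP Appendix 1 and the table shells were not in the text available, and might settle the contrast.

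**Conclusion.** Two points hold. First, the heart-rate MMRM has an uncentred baseline×treatment term, lacks the baseline×visit term of the SAP's other MMRMs, and names no contrast. A test at 0 beats/min is a risk rather than the stated plan. If it occurred, the SE would be about 6 to 14 times that at the mean baseline over the assumed range, and the sign could be wrong if the drug effect depends on baseline. An LS-means difference at the mean baseline avoids both.

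Second, both ECG models depart from SAP 4.2.4. Leaving out the strata does not bias the randomised comparison. It costs some precision, which was not quantified and may be modest given the narrow age range (4 to under 8 years) and the adjustment for baseline.

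Importance is low. These safety analyses are outside the hierarchy in SAP 4.2.5, and neither document states a decision rule that uses them.

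**What to change.** In SAP 4.13.5, before unblinding:

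1. State that the heart-rate test is the LS-means difference at Week 52, with by-visit differences also reported, evaluated at the mean (or centred) baseline heart rate.
2. Replace baseline×treatment with baseline×visit. If dependence of the effect on baseline is of interest, keep baseline×treatment in a separate, centred analysis labelled as effect modification.
3. Add baseline age, baseline time to stand, region and, where numbers allow, eteplirsen use to the heart-rate MMRM and the ECG ANCOVAs, as 4.2.4 requires. If the sponsor meant 4.2.4 for efficacy models only, it should say so there; that would remove the inconsistency but not recover the precision.
4. Name the MMRM or the ANCOVA as the main heart-rate analysis. With the MMRM as main, keep the Week 52 ANCOVA as supportive.

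The cost is a few sentences and a few lines of code, using data already collected. The one trade-off is that eteplirsen may have too few patients to estimate its term, so the SAP should say when it will be dropped.

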4.13.6. Cardiac Monitoring

Measures of cardiac autonomic dysfunction, including heart rate variability, will be measured at Screening, Week 26, and Week 52. Cardiac monitoring will be performed for approximately 48 hours remotely via a wearable cardiac monitoring device if approved for use in the participating country. Cardiac monitoring data analysis methods will be provided in a separate analysis plan.

4.13.7. Bone Evaluation

Lateral thoracolumbar spine radiography scans and Dual-energy X-ray absorptiometry (DXA) scans will be performed at Baseline and Week 52. In Germany, bone assessment will not be performed until the respective approvals from the German Federal Office for Radiation Protection become available. Bone radiography will be locally read and centrally evaluated. Bone evaluation data analysis methods will be provided in a separate analysis plan.

4.13.8. Prior and Concomitant Medications and Therapeutic Procedures

Prior and concomitant medications and therapeutic procedures will be coded using the WHO Drug dictionary. Results will be tabulated by Anatomic Therapeutic Class (ATC; level 4) and preferred term.

Prior medications are those that started and stopped before exposure to study medication (i.e., date of first dose); concomitant medications are all medications taken during the study period, including those started before but on going at first dose. Where a medication start date is partially or fully missing, and it is unclear as to whether the medication is prior or concomitant, it will be assumed that it is concomitant.

The use of concomitant medications will be included in a by-patient data listing and summarized in a table. The use of prior medications and therapeutic procedures will be included in by-patient data listing.

Additionally, a by-patient listing of concomitant medications that started or stopped during the treatment period will be created, specifically indicating the following:

- Treatment Group
- Patient ID:
- Medication Name/Preferred Term/ATC Term Modification:
- Indication

- Start/Stop Date (ongoing)
- Dose (unit)
- Frequency/Route

The determination of a medication starting or stopping with the treatment period will be based on the following:

- Date of First Exposure to Treatment \leq Date of medication start date \leq Date of Last Exposure to Treatment

(i.e., $ADCM.TRTSDT \leq ADCM.ASTDT \leq ADCM.TRTEDT$)

The following general rules will be used for partially missing medication start dates:

- If the start day is missing, but the start month and year are complete, the medication will be considered as having started during the treatment period if the month/year is between the treatment start/stop month/year values (inclusive).
- If the start day and month are missing, but the start year is complete, the medication will be considered as having started during the treatment period if the year is between the treatment start/stop year values (inclusive).
- If the start date is completely missing, the medication will not be considered as having started in the treatment period.

- Date of First Exposure to Treatment \leq Date of medication stop date \leq Date of Last Exposure to Treatment

(i.e., $ADCM.TRTSDT \leq ADCM.AENDT \leq ADCM.TRTEDT$)

The following general rules will be used for partially missing medication stop dates:

- If the stop day is missing, but the stop month and year are complete, the medication will be considered as having stopped during the treatment period if the month/year is between the treatment start/stop month/year values (inclusive).
- If the stop day and month are missing, but the stop year is complete, the medication will be considered as having stopped during the treatment period if the year is between the treatment start/stop year values (inclusive).
- If the stop date is completely missing, the medication will not be considered as having stopped in the treatment period.

Note: Here ADCM refers to the ADaM concomitant medications dataset. The words after “ADCM.” indicate variables in the ADaM concomitant medications dataset.

5. COVID-19 ASSESSMENTS AND RELATED ANALYSES

The following sections describe the COVID-19 related assessments collected and additional analyses to address the potential impact of COVID-19.

5.1. COVID-19 Site-Level Assessments

The following site-level information will be listed for each site impacted by COVID-19.

- Site Number
- Site Name
- Trial Activities Impacted by COVID: Yes, No
- Site Closed to Research: Yes/No
- Start/Stop Dates of Closure
- Site Open but Limited Capacity: Yes, No, NA
- Start/Stop Dates at Limited Capacity

This information will be collected by the sponsor and provided in an excel spreadsheet for incorporation into the database. Only sites impacted by COVID-19 will be included.

5.2. COVID-19 Patient-Level Listings

The following data will be listed to provide patient-level information on which assessments were impacted by COVID-19.

- Patient ID
- Visit Week
- Reason for Impact: This information will be collected via discussions with the site (and provided by the sponsor for incorporation into the database) examples of the responses will include:
 - Patient Discretion due to COVID
 - Site closed due to COVID
 - Travel Restrictions due to COVID
 - Reduced Capacity due to COVID
- Out of window visit:
 - Yes, No

A visit will be considered out of window if the difference between the date of visit and the scheduled date is outside of the ± 10 day window. The scheduled dates for the Week 26, 39, and 52 visits, are 182, 273, and 364 days from the patient's date of randomization, respectively. For this determination the date of NSAA assessment will be

used. If that date is missing, the date of the visit (i.e., from the DOV SAS dataset) will be used.

- Remote Visit:

- Yes, No

This will be determined by the “Telehealth Contact” variable in the Date of Visit eCRF page (i.e., Telehealth Contact value of “Yes” = Remote Visit = “Yes”; Telehealth Contact value of “No” = Remote Visit = “No”). Note for Week 26 this information will be provided in the spreadsheet (i.e., the “Remote Visit” Column).

- Re-supply Study Drug:

- Yes, No

This will be determined by the “Re-supply Study Drug” variable in the Date of Visit eCRF page. Note for Week 26 this information will be provided in the spreadsheet (i.e., the “Re-supply” column).

- Safety Lab:

- Yes, No

This will be determined by the “Safety Labs” variable in the Date of Visit eCRF page. Note for Week 26 this information will be provided in the spreadsheet (i.e., the “Safety Labs” column).

- Local Lab:

- Yes, No

This will be determined by the SAS variable LB.LOCALYN (i.e., from the eCRF Central Laboratory page “Were local labs used for this visit?”). Note for Week 26 this information will be provided in the spreadsheet (i.e., the “Local Labs” column).

- Height Collected, Weight Collected:

- Yes, No

If the patient’s height (weight) is non-missing for this visit, the value will be “Yes”, “No” otherwise

- Remote Efficacy:

- Yes, No

This will be determined by the “Remote Efficacy” variable in the Date of Visit eCRF page; a value of “Yes” indicates a response of “Remote”, a value of “No” indicates “Site”. Note there is no remote efficacy at Week 26 (i.e., for Week 26 Remote Efficacy = “No” should be populated in the listing).

- NSAA Performed, 10 MWT Performed, 4SC Performed, TTS Performed, Muscle Strength Performed:

- Yes, No

These variables will be determined by the “was the test performed variables” listed below:

Assessment	SAS Variable
NSAA Performed	MK_NSAA.MKPERF
10 MWT Performed	MK_TFT.WT_MKPERF
4SC Performed	MK_TFT.SCT_MKPERF
TTS Performed	MK_TFT.RFS_MKPERF
Muscle Strength Performed	MK_MST.MKPERF
PODCI Performed	QS_PODCI.QSPERF

- PE Collected, ECG Collected, PK Collected, Biomarkers Collected, Cardiac Monitoring Performed, DXA Performed, Spine Films Performed:
 - Yes, No

These variables will be determined by the “was the test performed variables” listed below:

Assessment	SAS Variable
PE Collected	PE.PEPPERF
ECG Collected	EG.EGPPERF
PK Collected	PC_BL.PCPPERF
Biomarkers Collected	PC_PD.PCPPERF
Cardiac Monitoring Performed	FA_CM.FAPERF
DXA Performed	PR_DXA.PROCCUR
Spine Films Performed	PR_LSR.PROCCUR

There is also a comment field.

Only assessments impacted by COVID-19 will be included.

5.3. COVID-19 Analyses

The primary and secondary efficacy analysis ([Sections 4.10.1](#) and [4.10.2](#)) will be repeated for the following two sensitivity analyses (i.e., a total of 8 new analyses: 2 sensitivity analyses across the primary and 3 secondary endpoints).

- 1) Excluding all remote efficacy assessments
- 2) Excluding all assessments which occurred during the time period the patient’s site was closed.

6. CHANGES TO PLANNED ANALYSES

The following are changes to the planned analyses as specified in the 16APR2020 version of the protocol:

- The MMRM model for the primary and secondary endpoint analyses was updated to include baseline covariate by study visit interaction terms and the Baseline age and Baseline time to stand are continuous variables (as specified in [Section 4.10.1](#)).
- An additional endpoint was added, the CFB rank sum score at Week 52. This endpoint is designed to assess the effect of edasalonexent versus placebo across multiple endpoints using a non-parametric rank-based approach. The endpoint is the sum of the ranks of the following Week 52 CFB scores: NSAA, 10MWT speed, stand from supine speed, 4-stair climb speed, and PODCI transfer and basic mobility scale.

8. CLINICAL STUDY REPORT APPENDICES

The set of tables and listings along with the corresponding shells will be provided in a separate document.
